3.3.3. Interruption or Discontinuation of Treatment

A reaction of at least moderate erythema (2) accompanied with mild, but definite edema (1) to a study product observed after the first patch application/irradiation sequence of the Induction Phase may indicate the subject to be pre-sensitized and may cause the discontinuation of the subject from the study.

After the second reading of the Induction Phase, either of the following conditions will require that the study product be applied to a naïve patch site under open patch conditions:

- Reaction of >50% “p” or “p” with no erythema, mild but definite erythema, moderate or severe erythema; or “D” (see [Table 3](#) and [Table 4](#));
- Any reaction of definite erythema (mild, moderate or severe) with definite edema.

Study product may not be relocated more than twice.

If the reactions noted above occur on an irradiation day during the Induction Phase, the sites will not be able to be irradiated. Patches will be relocated at the subject’s next visit.

The 3 weeks of continuous patch contact during the Induction Phase frequently results in tape-related irritation that is exacerbated by warm weather, but which occurs among some individuals irrespective of the season. Tape-related irritation will not be graded as a photosensitivity response at the patch site but will be noted separately on the case report form (CRF). Severe tape-related irritation will necessitate a change in the application site. As above, the application site will only be changed twice and then the subject must be discontinued.

One application/irradiation session may be missed during the Induction Phase. In case of a missed application/irradiation, an additional application/irradiation during Week 4 must be

performed. In this case, no evaluation will be required following irradiation. Only one missed patch application or irradiation is allowed. A subject must be discontinued and considered not complete if more than one application or irradiation is missed.

In accordance with legal requirements and ICH-GCP guidelines, every subject has the right to refuse further participation in the study at any time and without providing reasons (see also [Section 5.3](#)). A subject's participation is to be terminated immediately upon his/her request. The Investigator should seek to obtain the reason and record this on the CRF.

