After 24 hours (± 4 hours) of study product application (eg, Tuesday and Friday), all patches will be removed. The sites will be evaluated using the scoring system detailed in [Section 3.5.7.1](#). One set of patches will be assigned for irradiation and the other will remain non-irradiated, ie, only one application site of each study product will receive irradiation. On all Tuesdays and Fridays, the sites designated for irradiation will be irradiated with 2 times the subject's MED using the full Xenon lamp spectrum.

Adverse events and concomitant medications will be reviewed at each visit and recorded as applicable.

One application/irradiation session may be missed during the Induction Phase. If a subject misses an irradiation session during the Induction Phase, an additional application/irradiation session will be scheduled the Monday of rest period (week 4).

Rest Period (Weeks 4 and 5)

During the Rest Period of approximately 10-17 days, subjects will not receive any application of study materials. An additional application of study product may be applied on the Monday of the

rest period (week 4) if the subject misses an irradiation session during the Induction Phase of the study.

Challenge (Week 6)

On Day 1 of the Challenge Phase, subjects who have completed the Induction Phase and the Rest Period will have study product applications to naïve sites in the same manner as applied during the Induction. As in the Induction Phase, 0.2 g of MC2-01 Cream and MC2-01 Vehicle will each be applied to 4 assigned sites for Challenge for approximately 24 hours (± 4 hours) under semi-occlusive patch conditions. A baseline evaluation of the naïve sites will be performed immediately prior to application of the patches to ensure that no conditions, markings, or coloration of the skin will interfere with interpretation of the study results. The clinical staff will then remove the patches and a trained evaluator will evaluate the test sites. The designated sites and an additional untreated site will be irradiated with 6 J/cm² of UVA (320-400 nm) followed by 0.5 times the MED of UVA/UVB (full-spectrum) irradiation, obtained by using a filtered light source (see [Section 3.5.4](#)). Each site will be evaluated again at approximately 24 hours (± 4 hours), 48 hours (± 4 hours), and 72 hours (± 4 hours) post irradiation.

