4.3. Subject Populations for Analysis

All subjects who receive treatment will be evaluable for AEs. The analysis of local tolerability (photoirritation) will be based off all subjects who complete the Induction Phase of the study. Subjects who completed Induction are those who have received at least 6 applications/irradiation of study products, and at least 11 subsequent evaluations during Induction. The evaluation of photosensitization will be based on all subjects who complete the Challenge Phase of the study. Subjects who completed Challenge are those who have received at least 6 applications/irradiation of study products, and at least 11 subsequent evaluations during Induction, completed the Rest Phase and have received one application of study products at Challenge, subsequent irradiation and complete the 3 post-irradiation evaluations for that product.

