### **11.2.1. Population I**

Photosensitization potential for each test product site will be assessed only among subjects completing the Induction and Challenge Phases for that product. To be considered a complete case for a particular test product, a subject must have 6 applications/irradiation and no less than 11 **subsequent** readings during Induction, 10-17 days rest, and 1 application and at 3 post-irradiation evaluations during Challenge for that product. However, those subjects who demonstrate photosensitization, even though they have not completed all visits, will also be included in this population and will be evaluated. If subject's patch sites were discontinued because they were considered by the Investigator to be pre-photosensitized during Induction, this subject will not be included in this population for that test product.

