### **11.2.2. Population II**

Photoirritation potential for each test product will be assessed only among subjects completing the Induction Phase. To be considered a complete case for each test product, a subject must have 6 applications/irradiation as scheduled in the Induction Phase and no less than 11 **subsequent** readings as scheduled during the Induction Phase for that product.

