**MC2 Therapeutics**  
Protocol No. MC2-01-C10

Page X of Y

Table 14.2.1.1: Summary of Dermal Responses by Response Scores and Notations During Induction  
Population II

Response	MC2-01 cream		MC2-01 vehicle		Untreated
	Irradiated	Non-Irradiated	Irradiated	Non-Irradiated	Irradiated
Reading 1, n (%)					
Response Score (Sum of Erythema and Edema)					
0	xx (xx.x)	xx (xx.x)	xx (xx.x)	xx (xx.x)	xx (xx.x)
1	xx (xx.x)	xx (xx.x)	xx (xx.x)	xx (xx.x)	xx (xx.x)
1 Hr	xx (xx.x)	xx (xx.x)	xx (xx.x)	xx (xx.x)	xx (xx.x)
2	xx (xx.x)	xx (xx.x)	xx (xx.x)	xx (xx.x)	xx (xx.x)
etc.	xx (xx.x)	xx (xx.x)	xx (xx.x)	xx (xx.x)	xx (xx.x)
[Reading 2, n (%)] to [Reading 11, n (%)]					
Response Score					
0	xx (xx.x)	xx (xx.x)	xx (xx.x)	xx (xx.x)	xx (xx.x)
etc	xx (xx.x)	xx (xx.x)	xx (xx.x)	xx (xx.x)	xx (xx.x)

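### SAP 11.2.2 read literally drops from the photoirritation analysis a subject who uses the one permitted make-up session, and can drop strong reactors

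*SAP*

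**What the plan says.** - **Population II (SAP 11.2.2).** To be a complete case for a product, "a subject must have 6 applications/irradiation as scheduled in the Induction Phase" and have no less than 11 "readings as scheduled during the Induction Phase for that product".
- **Population I (SAP 11.2.1).** Here "a subject must have 6 applications/irradiation and no less than 11" readings during Induction. The qualifier *as scheduled* is absent, and "those subjects who demonstrate photosensitization, even though they have not completed all visits, will also be included in this population".
- **Protocol 4.3.** Completers of Induction have at least 6 applications/irradiations and "at least 11 subsequent evaluations during Induction". The qualifier is absent here too. SAP section 12 nevertheless declares no changes from the protocol.
- **Protocol 3.3.3.** "One application/irradiation session may be missed during the Induction Phase". A Week 4 make-up is then mandatory, and a subject is discontinued and counted as not complete only if more than one application or irradiation is missed. A site with a qualifying strong reaction on an irradiation day is not irradiated, and the patch is relocated at the next visit.
- **Protocol 3.5.1.** After a missed irradiation, "an additional application/irradiation session will be scheduled the Monday of rest period (week 4"). Table 2 provides an evaluation at both the make-up application visit and the make-up irradiation visit.

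No section says whether the make-up session and its readings count towards the 6 and the 11, or whether those readings enter the Induction mean score.

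**The concern.** Two rules meet at the same subject and disagree. The protocol builds in one make-up so that a single missed session does not end a subject's participation. The SAP's definition of Population II then asks for the full Weeks 1-3 schedule. A programmer who follows SAP 11.2.2 excludes the make-up user; one who follows protocol 3.3.3 keeps that subject. If this is left open until treatment codes are merged, population membership would be settled with results in view.

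The second consequence is more troubling because it depends on the outcome. A product site that reacts strongly on an irradiation day loses that irradiation. Read literally, the product then lacks one of its six scheduled irradiations, and the subject is not a complete case for it. The highest irritation scores are the ones at risk of leaving the mean. Population II feeds the Induction ANOVA and its pairwise p-values, the only hypothesis tests in the plan.

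**Working it through.** **1. Reproduce the figure of 11.** From protocol Table 2, applications are on Days 1, 4, 8, 11, 15 and 18, and irradiations on Days 2, 5, 9, 12, 16 and 19. Post-application readings therefore fall on Days 2, 4, 5, 8, 9, 11, 12, 15, 16, 18 and 19. That is 11, with none after the last Friday irradiation. SAP Table 14.1.3 lists the same days. The minimum equals the schedule, so there is no slack.

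**2. Take away one session, then add the make-up.** Day 1 is a Monday, so the Week 4 Monday is Day 1 + 21 = 22 and the make-up irradiation about 24 hours later is Day 23. Each visit carries one reading.

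| Missed | Sessions in Weeks 1-3 | Readings in Weeks 1-3 | Sessions with make-up | Readings with make-up |
|---|---|---|---|---|
| Irradiation visit only | 5 | 10 | 6 | 10 + 2 = 12 |
| Application visit only (sessions 2-6) | 5 | 10 | 6 | 10 + 2 = 12 |
| Both visits (sessions 2-6) | 5 | 9 | 6 | 9 + 2 = 11 |

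Session 1 differs slightly because Day 1 is not a reading day. Missing both its visits leaves 10 readings; missing Day 1 alone leaves 11, but still only 5 sessions.

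Counting Weeks 1-3 only, every make-up user fails. Counting the make-up and both its readings, every make-up user passes. One make-up reading is not always enough: 9 + 1 = 10 fails.

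**3. Does the rest interval fit?** Challenge starts on Day 36. Without a make-up the interval is 36 - 19 = 17 days; after a make-up irradiation it is 36 - 23 = 13 days. Both lie within the 10-17 days allowed, so the timetable accommodates make-up users.

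**4. Size, as an illustration.** The documents give no miss rate. Assume a probability p of missing each of the 11 reading visits, independently. Each is also an application or irradiation visit. The chance of missing exactly one is 11 × p × (1 - p)^10:

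- p = 1%: 0.11 × 0.904 = 9.9%
- p = 2%: 0.22 × 0.817 = 18.0%
- p = 5%: 0.55 × 0.599 = 32.9%

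A subject who misses both visits of one session is also a make-up user. Over sessions 2-6 that adds 5 × p² × (1 - p)^9, which at p = 5% is 5 × 0.0025 × 0.630 = 0.8 percentage points.

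**5. The reactor route.** Under protocol 3.3.3 the site may still be read, so the reading count need not fail. What fails is the count of six scheduled irradiations. No section says whether an irradiation withheld for a reaction is a missed one, or whether a make-up restores it. SAP 11.2.1 has an exception for incomplete subjects who show photosensitization; SAP 11.2.2 has none. The documents give no rate for such reactions, so the bias has a direction but no calculable size.

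**The case against.** The strongest reply is that the documents plainly intend make-up users to be completers. Protocol 3.3.3 sets the limit at more than one missed session. The make-up is itself described as scheduled. Protocol 3.1 treats the last make-up visit like the last Induction Friday, with no reading after irradiation. Table 2 provides readings at both make-up visits, and the rest interval fits. All of this stands as evidence of intent. It does not change SAP 11.2.2, which ties both counts to the Induction Phase, whereas the make-up is scheduled in the Rest Period.

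A reader might also infer stronger points that the documents do not support:

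- **Exclusion from the photosensitization population.** SAP 11.2.1 and protocol 4.3 lack *as scheduled*. Their phrase *during Induction* leaves the status of the make-up open; it does not settle an exclusion.
- **Photosensitization incidence biased downward.** SAP 11.2.1 keeps incomplete subjects who demonstrate photosensitization. Keeping incomplete positives while dropping incomplete negatives would, if anything, raise the proportion.
- **A loss of 10%, 20% or 43%.** That is 1 - (1 - p)^11 at the same assumed rates: the chance of missing any visit. It includes subjects who miss more than one session, whom protocol 3.3.3 discontinues on any reading.
- **No room for make-up readings in the SAP outputs.** The Induction shells number readings from 1 to 11 and not by day, so a subject with 9 + 2 readings fits, and Listing 16.2.6.1 is open-ended. What is missing is a make-up row in Table 14.1.3 and a place for a twelfth reading.

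It is also fair to say that SAP 11.1 calls the Induction analysis supportive. Photosensitivity is diagnosed by the Investigator and not by a statistical test, so the primary question does not rest on Population II.

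**Conclusion.** The point holds for Population II. On its literal wording, SAP 11.2.2 excludes a subject who misses one session and completes the required make-up, in conflict with protocol 3.3.3. It adds a qualifier that protocol 4.3 lacks while SAP section 12 declares no change. It can also remove strong reactors from the irritation analysis and so bias irritation scores downward. For Population I there is an ambiguity to close, not a demonstrated exclusion or bias.

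About 10%, 18% or 33% of subjects would be affected through a single missed visit if per-visit miss rates were 1%, 2% or 5% and independent. Both the rates and the independence are assumptions, and the figures apply only if make-ups are not counted. The reactor effect cannot be sized from the documents. The analysis at stake is supportive, but the correction is cheap and should be made before database lock.

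**What to change.** 1. In SAP 11.2.2 only, delete *as scheduled* in both places.
2. In SAP 11.2.1 and 11.2.2, state that the Week 4 make-up application/irradiation counts towards the 6 and that its two readings count towards the 11. State in SAP 11.7 that these readings enter the Induction mean score.
3. Add a make-up row to Table 14.1.3, and a note to the Induction shells on where a twelfth reading is shown.
4. For analysis membership only, keep in Population II a subject whose site was not irradiated because of a reaction, using all available readings without imputation, in line with SAP section 8. Reconcile this with the missed-session limit in protocol 3.3.3 by stating whether such an irradiation counts as missed for the population definitions. The clinical rule itself is not altered.

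The cost is a few sentences and one table row. No visits, procedures or data are added.

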### **11.2.3. Population III**

This population will include all subjects who received the study products. This will also be the population used for adverse events analyses.

## **11.3 Subject Disposition**

The number of subjects screened, randomized, completing the Induction phase, completing the Challenge phase, included in the analysis of photosensitization (Population I), included in the

---

***Statistical Analysis Plan***

---

analysis of photoirritation (Population II), included in the analysis of adverse events (Population III) and discontinued (by reason for discontinuation) will be summarized using descriptive statistics.

**11.4 Background and Demographic Characteristics**

Descriptive statistics will be used to summarize demographic characteristics (i.e., age, gender, ethnicity, and race) and background characteristics (i.e. Fitzpatrick skin type and MED) for the randomized subject population. Past/coexistent medical history information for all randomized subjects will be presented in a by-subject listing. Urine pregnancy test results will be presented in a by-subject listing.

**11.5 Study Products/Visit Compliance**

Descriptive statistics will be used to summarize study product compliance for the randomized subject population.

**11.6 Prior and Concomitant Therapy**

Prior and concomitant medication information for all randomized subjects will be presented in a by-subject listing.

**11.7 Dermal Response Evaluation**

The following scoring grades and notations will be used for the evaluation of dermal response at each application and control site throughout the Induction and Challenge Phases of the study. Tape related irritation will not be graded as an irritant response at the patch site.

***Statistical Analysis Plan***

**Grading of Responses**

Response	Symbol	Numerical Equivalent Score
Erythema		
No reaction	-	0
Mild, but definite erythema	+	1.0
Moderate erythema	++	2.0
Marked/severe erythema	+++	3.0
Edema		
No reaction	0	0
Mild, but definite edema	**	1.0
Definite edema with erosion/vesiculation	***	2.0

**Response Notations**

Response/Comment	Notation
Hyperpigmentation	Hr
Hypopigmentation	Ho
Vesiculation	V
Papular response	p
Papulovesicular response	pv
Damage to epidermis: oozing, crusting and/or superficial erosions	D
Itching	I
Spreading of reaction beyond patch study site (i.e., reaction where material did not contact skin)	S
Follicular irritation with or without pustule formation (folliculitis)	f
Subject absent	X
Patch dislodged	PD
Not patched	NP
No reaction	0

Note: The numerical score for edema is to be added to the numerical score for erythema. The literal notations in the second part of the table are not associated with additional numerical value.

All assigned scores during the study will be summarized using frequency counts by treatment at each time point. Erythema and edema scores will be summarized separately. All pairwise comparisons will be performed on the mean of the Induction Phase response scores using Fisher's least significant differences in the analysis of variance (ANOVA) with effects of subjects and treatment. The response score for each subject will be calculated by summing the erythema and edema score and then the mean of the response scores at each reading during the Induction Phase will be calculated for the subject. Pairwise differences will be tested only if the null hypothesis of a common mean score for all products is rejected at the 5% level.

---

*Statistical Analysis Plan*

---

In case of gross violations of the model assumptions (normality, homoscedasticity), non-parametric analysis will be performed. All assigned scores during Induction for each product will be ranked within subject and compared pairwise using Wilcoxon signed-rank test. Pairs to be compared include each test sample irradiated versus non-irradiated and all pairwise comparisons on each side.

## **11.8 Safety Evaluation**

### **Assessment of Photosensitization Response**

The determination of dermal photosensitization potential will be based on specific scoring criteria derived from observations in the Challenge Phase of the study and confirmed in the Rechallenge Phase, if necessary. Criteria specified in the study protocol may cause the continuation of a subject into the Rechallenge Phase of the study. The diagnosis of a photosensitization response will be made by the Investigator based on review of the observed skin responses after Challenge. Photosensitivity will not be determined by statistical methods. All assigned scores during induction and challenge will be summarized by frequency counts by time point and treatment. The incidence of photosensitization reactions will be summarized by frequency counts for each treatment.

### **Local Tolerability Assessments**

The mean numerical equivalent score by subject and treatment, including all scores assigned during induction, will be analyzed in the analysis of variance (ANOVA) with factors subject and treatment. Selected pairwise comparisons will be performed in the context of the ANOVA. Pairs to be compared are: each test sample irradiated versus non-irradiated (MC2-01 cream irradiated versus non-irradiated; vehicle irradiated versus non-irradiated, and untreated control irradiated versus non-irradiated) and all pairwise comparisons on each side (MC2-01 cream versus vehicle; MC2-01 cream versus untreated control; and vehicle versus untreated control; all on both the irradiated and non-irradiated sides).

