3.4.5. Assignment to Treatment

3.4.5.1. Randomization

Each subject who signs an informed consent form (ICF) will be assigned a screening number. If the subject meets all of the inclusion and none of the exclusion criteria, and successfully completes the screening procedures, they will be enrolled in the study. Upon enrollment, each subject will be assigned a unique subject number and receive a randomization code, indicating application placement of the study materials. Each subject in this study will serve as his or her own control. All subjects will receive MC2-01 Cream and MC2-01 Vehicle at adjacent application sites, i.e. study product placement on the left side will be the same as on the right side.

The MC2-01 Cream and MC2-01 Vehicle will be assigned in a randomized sequence to the test sites. The same study material will be applied to the same test site throughout the Induction Phase and to a naïve site at Challenge and Rechallenge Phases (if applicable).

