**MC2 Therapeutics**  
Protocol No. MC2-01-C10

Page X of Y

Listing 16.1.7: Subject Randomization  
All Randomized Subjects

Subject Number	Informed Consent Date	Met all Inclusion/Exclusion Criteria?	Randomization Date	Randomization Number	Randomization [1]	
					Site 1	Site 2
XX	XXXX-XX-XX	Yes	XXXX-XX-XX	XX	A	B
XX	XXXX-XX-XX	Yes	XXXX-XX-XX	XX	B	A
XX	XXXX-XX-XX	Yes	XXXX-XX-XX	XX	A	B
XX	XXXX-XX-XX	Yes	XXXX-XX-XX	XX	B	A
XX	XXXX-XX-XX	Yes	XXXX-XX-XX	XX	B	A

[1] A = MC2-01 cream; B = MC2-01 vehicle

Generated on XX/XX/XX:XXXX by XXXXXXXX / Uses: XXXX, XXXX

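### The Induction ANOVA has no term for the randomized site position, so any Site 1–Site 2 difference inflates its error and, if the two placement orders are unequal in number, shifts the cream–vehicle estimate by chance

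*SAP*

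**What the plan says.** Protocol 3.4.5.1 describes the randomization as one of placement: "The MC2-01 Cream and MC2-01 Vehicle will be assigned in a randomized sequence to the test sites". It adds that "study product placement on the left side will be the same as on the right side" and that "The same study material will be applied to the same test site throughout the Induction Phase". The shell of SAP Listing 16.1.7 records the result for each subject in two columns, Site 1 and Site 2, with the key "A = MC2-01 cream; B = MC2-01 vehicle". So there are two orders, AB and BA.

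SAP 11.8 (Local Tolerability Assessments) analyses the mean Induction score per subject and treatment in an "analysis of variance (ANOVA) with factors subject and treatment". SAP 11.7 says the same: "analysis of variance (ANOVA) with effects of subjects and treatment". Protocol 4.1 and 4.6.1 and the footnotes to SAP Table 14.2.1.2 name the same two effects. None of them has a position, site or sequence term, and neither does the Wilcoxon signed-rank fallback in SAP 11.7. Pairwise tests follow an overall test: "Pairwise differences will be tested only if the null hypothesis of a common mean score for all products is rejected at the 5% level".

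Neither document states an allocation ratio or blocking for AB against BA. The ANOVA uses subjects who complete Induction (Population II, SAP 11.2.2). SAP 11.1 calls the analysis supportive and says that photosensitivity is not determined by statistical methods.

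**The concern.** Within a subject, cream minus vehicle equals the product effect plus d in one order, and the product effect minus d in the other, where d is the Site 1–Site 2 difference. The subject factor removes differences between subjects but not this one. Because a product does not move between the two positions by design, averaging the Induction readings does not remove it either.

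Two things follow. For any non-zero d, the planned residual contains position variation that a recorded factor could explain. And unless the analysed subjects split exactly evenly between AB and BA, the cream–vehicle estimate carries part of d. Equal allocation at randomization would not guarantee an even split among completers.

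What is at stake is the precision and the stated SE of the Induction comparisons. Irritation during Induction is a named safety endpoint (Protocol 3.1, SAP 3), and this ANOVA, with its fallback, is its only inferential analysis.

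**Working it through.** **No figure to reproduce.** The plan justifies 50 evaluable subjects by convention (Protocol 4.2, SAP 11.9) and gives no SD, effect size, power or position effect. What follows is therefore a range under stated assumptions.

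**Inputs.**
- From the documents: n = 50; four product sites per subject in Induction (cream and vehicle, each irradiated and non-irradiated); effects of subject and treatment only.
- Assumed: SD of the per-subject cream–vehicle difference within an order, 0.4 to 0.6 score units; d, 0.1 to 0.3; the same order in both sets; equal, independent site residuals with SD σ = SD of difference/√2, so σ² = 0.08 to 0.18.
- The untreated column in the Induction table shells is left out, because Protocol 3.1 marks and irradiates that site only at Challenge.

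**Shift of the estimate.** With n1 subjects having cream at Site 1 and n2 at Site 2, the shift is d × (n1−n2)/n.
- 25/25: 0. 28/22: 0.12d. 30/20: 0.20d.
- Under simple randomization the shift has mean 0 and SD d/√50 = 0.14d, which is 0.014 for d = 0.1 and 0.042 for d = 0.3. Exact 25/25 balance then has probability 11.2%.

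**Error term under equal allocation.** Each of a subject's four sites carries +d/2 or −d/2, so position contributes 4 × d²/4 = d² per subject and nd² in total. None of it is absorbed by subject or treatment. Spread over 3(n−1) = 147 df:

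residual mean square = σ² + 50d²/147

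SE ratio = √(1 + 50d²/(147σ²))

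| SD of difference | σ² | d = 0.1 | d = 0.2 | d = 0.3 |
|---|---|---|---|---|
| 0.4 | 0.08 | 1.021 | 1.082 | 1.176 |
| 0.6 | 0.18 | 1.009 | 1.037 | 1.082 |

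The planned SE is thus about 0.9% to 18% larger than it would be without the position effect.

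**What this does to the test.** Simulation with 20,000 trials per setting: two-sided 5% tests of cream against vehicle within one set, without the overall F gate, SDs and SEs in units of σ. The assumed inputs correspond to d/σ from 0.1/√0.18 = 0.24 to 0.3/√0.08 = 1.06, so the rows for 0.25 and 1 are close to the two ends.

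| Allocation | d/σ | True SD | Planned SE | Type I error | Power at 0.5σ | Power with position |
|---|---|---|---|---|---|---|
| 25/25 | 0.25 | 0.201 | 0.202 | 4.7% | 69% | 70% |
| 25/25 | 0.5 | 0.199 | 0.208 | 3.9% | 67% | 70% |
| 25/25 | 1 | 0.200 | 0.2315 | 2.2% | 58% | 69% |
| Simple | 0.25 | 0.203 | 0.202 | 5.2% | 69% | 69% |
| Simple | 0.5 | 0.212 | 0.208 | 5.2% | 66% | 70% |
| Simple | 1 | 0.244 | 0.231 | 6.4% | 57% | 69% |

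With a position factor, the SE returns to 0.200–0.201σ and type I error to 4.6–5.1% in every setting. A fixed 28/22 split at d = σ shifts the unadjusted estimate by 0.12σ and the adjusted one by at most 0.001σ.

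**Irradiated against non-irradiated, same product.** With a shared order, position cancels from this estimate. The pooled error is still inflated, and type I error is 2.3–2.6% at d = σ.

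**The case against.** The case for leaving the model alone is a fair one.

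- **The position effect may be negligible.** The sites are adjacent, 2 cm × 2 cm, in one area of the back. The 18% figure needs a d equal to 75% of the SD of the difference (0.3/0.4). At d of about 0.25σ nothing of note changes. This stands, and it is why the gain is uncertain.
- **A reader might infer that the cream–vehicle estimate is biased.** The documents do not support this. Products are randomized to sites and treatment is in the model, so the estimate is unbiased over randomizations, and under an even split the shift is exactly zero. Silence on blocking does not show simple randomization either, since the randomization list is a separate document. Under an even split the planned test is conservative, not invalid.
- **A reader might compute √(1 + d²/SD²) and report an SE inflation of 1.4% to 25%.** That formula fits a separate paired analysis of one cream–vehicle difference. The SAP plans a pooled ANOVA, for which the same inputs give 0.9% to 18%.
- **A reader might infer that the photoallergy conclusion is at risk.** It is not: the diagnosis is the Investigator's, from Challenge and any Rechallenge.
- **Position is not perfectly defined.** Listing 16.1.7 has two site columns for four Induction sites. The left/right wording in Protocol 3.4.5.1 could refer to Induction against Challenge, since Protocol 3.1 puts these on opposite sides of the back. Protocol 3.3.3 also allows relocation of a product up to twice. These points stand, but they call for a definition in the SAP rather than for leaving the term out.

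**Conclusion.** The point holds as an optional gain in precision for a supportive analysis. The omission itself is certain: no description of the Induction ANOVA has a position term, although position is randomized and recorded. The excess error exists for any non-zero d; the shift of the estimate exists only when the analysed AB/BA split is unequal.

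The size is uncertain, because the documents supply neither d nor an SD. The 0.9% to 18% range for the SE holds for equal allocation, and the SD of 0.014 to 0.042 for the chance shift holds for simple randomization, both on the inputs assumed above. Nothing here is a flaw in the primary conclusion.

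**What to change.** - In SAP 11.7 and 11.8, add position as a fixed factor in the Induction ANOVA. Define it as the position assigned at randomization (Site 1 or Site 2), regardless of later relocation, and say how the two columns of Listing 16.1.7 map to the irradiated and non-irradiated sets.
- Make the fallback for cream against vehicle account for position. One way is to take each subject's Site 1 minus Site 2 difference and compare it between the AB and BA orders with a rank-sum test. Position is common to both groups and drops out.
- State whether AB/BA allocation is balanced, and list the added term in SAP section 12 as a change from the protocol analysis.

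The cost is one model term, a few sentences settled before unblinding, and 1 error df out of 147 (2 if position is fitted separately in each set). If the position effect is small, there is little or no gain.
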